## 12b. Statistical methods

As a reminder, the sample-size is designed to support a factor analysis for the hand-hygiene component of the project. The surface cleaning component of the project will only be analyzed using descriptive and exploratory methods.

Software: The data will be analysed using the most recently available copies of SPSS and SPSS: AMOS.

Descriptive: Frequencies, percentages, averages and confidence intervals will be used to describe the participants' responses and demographics.

Internal Consistency: Cronbach's alphas will be calculated. Items will be removed as necessary to achieve an alpha coefficient of 0.70 or above within each domain; those coefficients as low as 0.65 will be tolerated if necessary to retain the planned model.

[figure not shown]
Confirmatory Factor Analyses (CFA) - Objective 4: CFA will be performed to test whether the data from the items fit within the pre-determined components.

The first models (the primary analyses) will be conducted with the data from all the countries and then additional models (the secondary analyses) will be conducted with each country.

The models will be specified in AMOS and tested for goodness of fit using three indices: (a) absolute fit (based on a Chi-squared to degrees of freedom ratio, less than 2; ), (b) parsimony (based on Root Mean Square Error of Approximation (RMSEA) of close to or less than 0.06), and comparative fit (based on an index 'close to' 0.95; ). The models may be revised until the desired measures of fit are obtained.

Figure will be created to describe the final models' structure. An example of a figure like this with only 2 determinates appears below (Figure 2):

Figure 2. Example of a CFA model

Regression analyses - Objective 5: Multiple regression analysis will be conducted, overall and for each country. The predictors will be participants' average responses to each behavioural determinate, and the outcome will be participants' average responses to the confidence items. An alpha value of 0.05 will be used to assess each predictors' contribution to the overall model.

Exploratory Analyses - Objective 6: The participants' individual differences will be compared using graphical analyses (bar charts with error bars) and statistical tests (e.g., ANOVAs). Their content is not further specified within this protocol.

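### The primary CFA may be revised on the same data until it fits, with no conclusion stated if the pre-specified model misses its targets and no duty to report that model's fit

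*Combined protocol and SAP*

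**What the plan says.** The primary hypothesis (section 5a) is that the TDF domains account well for the hand-hygiene responses. Section 12b gives the analysis that bears on it:

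- Purpose: "CFA will be performed to test whether the data from the items fit within the pre-determined components".
- Data: "The first models (the primary analyses) will be conducted with the data from all the countries". Country-specific models follow as secondary analyses.
- Targets: (a) absolute fit, "based on a Chi-squared to degrees of freedom ratio, less than 2"; (b) "Root Mean Square Error of Approximation (RMSEA) of close to or less than 0.06"; (c) "comparative fit (based on an index 'close to' 0.95".
- Response to misfit: "The models may be revised until the desired measures of fit are obtained".
- Item removal, on Cronbach's alpha: "Items will be removed as necessary to achieve an alpha coefficient of 0.70 or above within each domain". An alpha down to 0.65 is accepted where that is needed to keep the planned structure.
- Output: "Figure will be created to describe the final models". No other CFA output is named.

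The abstract and section 11 say that a pilot survey informed the choice of items. The heading of Appendix A gives the items as final on 9 April 2020. It lists exactly three hand-hygiene items in each of the 11 domains, 33 in all.

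**The concern.** A confirmatory test needs a model fixed in advance and an outcome that counts against it. Here the model is fixed, but missing a target leads only to another model. A model adjusted to the data by which it is then judged is biased towards good fit, and its fit no longer tests the structure specified beforehand.

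Four things that would protect the test are absent from the plan: a limit or criterion for revisions, a hold-out or split sample, a conclusion if the pre-specified model misses, and a requirement to report that model's fit. Nor are revised models labelled exploratory.

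The targets do not form one pass/fail rule either. Only (a) is exact. Targets (b) and (c) accept values near a cut-off without saying how near, the comparative index is not named, and nothing says how the three combine.

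At stake is the answer to the primary hypothesis. The results are meant to inform a future school-based intervention, and a reader might never learn whether the structure set out in advance fitted.

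**Working it through.** The core point rests on the wording. The arithmetic shows whether the revision clause is likely to be used.

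**Inputs.** Table 2: India 375 + 375 + 75 = 825; each of six other countries 225 + 225 + 75 = 525. Pooled N = 825 + 6 × 525 = 3,975 at full recruitment. Appendix A: 33 items, 11 domains. Assumed specification: each item loads on its own domain only, factors freely correlated, normal-theory maximum likelihood, no item removed.

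**Degrees of freedom.** Moments: 33 × 34/2 = 561. Parameters: 22 loadings + 11 factor variances + 33 error variances + 55 factor covariances = 121. df = 561 − 121 = 440.

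**Targets (a) and (b) on one scale.** RMSEA = √[(χ²/df − 1)/(N − 1)]. Setting χ²/df = 2 gives RMSEA = √[1/(N − 1)]. Setting RMSEA = 0.06 gives χ²/df = 1 + 0.0036(N − 1).

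| Data | N | RMSEA at χ²/df = 2 | χ²/df at RMSEA 0.06 |
|---|---|---|---|
| Pooled | 3,975 | 0.0159 | 15.31 |
| India | 825 | 0.0348 | 3.97 |
| Each other country | 525 | 0.0437 | 2.89 |

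Pooled, (a) requires χ² below 2 × 440 = 880, while RMSEA 0.06 corresponds to χ² of about 440 × 15.306 = 6,735.

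**Chance of meeting (a), pooled.** χ² is taken as noncentral with 440 df and noncentrality (N − 1) × 440 × RMSEA². At a population RMSEA of 0.015 the chance is 0.83. At 0.02 the noncentrality is 3,974 × 440 × 0.0004 = 699.4 and the chance is 2.3 × 10⁻⁶. A model well inside (b) would then almost surely miss (a).

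**Illustrations on assumed loadings.** The documents give no expected misfit. The following are population calculations without sampling, with trait loading 0.66, factor correlations 0.4 and 0.6, and expected χ²/df = 1 + (N − 1)F₀/440, where F₀ is the population discrepancy.

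1. *TDF structure true, plus one wording factor on the 17 reverse-scored items.* Expected pooled χ²/df is 1.1 at wording loading 0.10, 1.3 at 0.15, 1.95 at 0.20, 3.0 at 0.25, 4.5 at 0.30 and 8.9 at 0.40. It passes 2 at a loading of about 0.20. At 0.25, RMSEA is 0.022 and CFI 0.974–0.979.
2. *TDF assignment wrong for k of the 33 items.* The a priori model gives:

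| k | χ²/df | RMSEA | CFI |
|---|---|---|---|
| 1 | 2.1–2.9 | 0.017–0.022 | 0.97–0.99 |
| 3 | 4.2–6.7 | 0.028–0.038 | 0.92–0.96 |
| 6 | 7.3–12.3 | 0.040–0.053 | 0.84–0.93 |

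A model with those k items moved has expected χ²/df of 1.0. That is so by construction, because the revision is set to the model that generated the data.

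**The case against.** The clause is permissive, and the specified models are fitted and compared with the targets before any revision. Revising a model is ordinary when a survey is being developed, which section 2 gives as a purpose. The sentence about final models concerns a figure, not which fit statistics are published. All of this stands, but it does not supply a conclusion for a missed target or a duty to report. The pilot was the item-selection stage, and Objective 2 calls this analysis confirmatory.

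Four stronger readings are tempting, and the documents do not support them:

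- *That the a priori fit will be withheld, or that revision is certain.* Reporting is neither required nor excluded, and the actual misfit is unknown.
- *That removing items on alpha contradicts section 12a.* Its three-item minimum describes the questionnaire, and Appendix A meets it. A deletion would leave a domain with at most two items, which weakens that rationale but does not contradict it. The 0.65 tolerance leans towards keeping the planned structure, though only for alpha.
- *That the misassigned-item figures show what revision would hide.* They depend on target (a). With RMSEA of 0.06 or less and CFI of 0.95 or more, the a priori model passes unrevised in three of the six cases: k = 1 at both correlations, and k = 3 at correlation 0.6 (CFI 0.963).
- *That chance overfitting would be large at the pooled N.* There are 330 cross-loadings + 528 error covariances = 858 one-parameter changes. Treated roughly as independent null chi-squares, the best 20 remove about 138 units, which takes a ratio of 1.0 to (440 − 138)/420 = 0.72. From 4.2 they would reach only (4.2 × 440 − 138)/420 = 4.1. The problem is labelling and reporting.

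**Conclusion.** The point holds and should be corrected before analysis, because it concerns the primary hypothesis. As written, that hypothesis has no stated way to fail, and a model selected on its own fit could be reported as confirming the TDF structure. That revision would use the same data is an inference, but a sound one, since no second or split sample is described.

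The conflict between targets (a) and (b) makes use of the clause plausible: at the planned pooled N, any model with RMSEA between about 0.016 and 0.06 meets one and misses the other. The conflict is smaller within countries. These figures assume the 33-item, simple-structure model and full recruitment; removing items, or a country stopping at 30 days, would change them. The wording-factor and misassigned-item results are illustrations only.

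**What to change.** In section 12b:

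1. State that the primary conclusion rests on the pre-specified 11-factor, 33-item model, with all items retained, fitted once to the pooled data and reported with all fit indices whatever the result. If it misses the rule, the primary hypothesis is reported as not supported.
2. Replace the sentence that permits revision with a statement that any revised model, pooled or by country, is exploratory, lists every change, and is reported beside the a priori fit.
3. Report alphas descriptively for the primary model.
4. Before data are seen, name the comparative index, give numeric cut-offs, state how they combine, and reconcile the chi-squared/df and RMSEA targets at this N. One example is RMSEA of 0.06 or less and CFI of 0.95 or more, with chi-squared/df reported without a cut-off.
5. If chi-squared/df below 2 stays a required target, state its price: at the pooled N, under the loadings assumed above, a reverse-wording effect with a loading of about 0.20 or more would have a true TDF structure reported as not supported.

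The cost is wording only, since the a priori model is fitted in any case. Revision remains allowed. The sponsor must accept that the a priori model may be reported as not fitting. Dropping the chi-squared/df cut-off removes the strictest target: the RMSEA allowed at the pooled N rises from below about 0.016 to 0.06, and a structure with a few wrongly assigned items could pass.

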#### 5b. Secondary Analysis

The first secondary hypothesis relates to Objective 2.

The TDF determinates will also describe the hand-hygiene data well across each country/region.

The second secondary hypotheses relates to Objective 3.

The TDF determinates will predict participants' hand-hygiene related self-reported confidence in influencing children's hand hygiene well as a whole and across each country/region.

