Appendix A presents a list of the domains, their definitions, and survey items about hand-hygiene influencing.

The hand hygiene items will appear in a random order.

In the final survey, we aim to assess each of 11 behavioral determinates using at least 3 items that can be responded to with a 5-point Likert scales, where 1=strongly disagree and 5=strongly agree. Some items will be reverse scored to mitigate acquiescence bias.

- **Survey Section 4: Surface disinfecting.**

Appendix A presents a list of the domains, their definitions and survey items about hand-hygiene influencing.

The surface cleaning items will appear in a random order.

In the final survey, we aim to assess each of 11 behavioral determinates using at least 1 item that can be responded to with a 5-point Likert scales, where 1=strongly disagree and 5=strongly agree. Some items will be reverse scored to mitigate acquiescence bias.

- **Survey Section 5: Self-reported confidence (3 items).**

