Appendix A also includes three self-confidence items.

The first item regards participants' confidence about how often their children clean their hands when they are present, 0% to 100% of the time. The second item regards participants' confidence about how often their children clean their hands when they are not present, 0% to 100% of the time. The third item regards participants' confidence about how often they clean their own hands, 0% to 100% of the time.

*Translation.*

After creating the initial items in the English language, the research team will ask OpinionHealth to translate them. The same process will occur for the information/consent sheet. The translation process will proceed as describe in Table 1.

Table 1. Translation process

Step	Action
1	The research team will provide OpinionHealth with the initial items.
2	OpinionHealth will translate the items into the non-English language(s)
3	OpinionHealth will back-translate the items to English.
4	OpinionHealth will provide the research team with copies of the translated and back-translated items.
5	The research team will check to be sure that the items' intended meanings have not been lost in translation. If items' meaning are lost, the translation process will be repeated with those items.

---

Opinion is a reputable survey company located in the United Kingdom experienced in conducting online surveys in line with all UK and EU regulations and Market Research Society's Code of Conduct, e.g., GDPR. For more information, a link to Opinion Health's website is provided here:  
[http://opinionhealth.com/about\\_us](http://opinionhealth.com/about_us)

*Active survey.*

OpinionHealth will to recruit participants according to a stratified fashion across countries and demographic characteristics, see Table 2.

Table 2. Participants stratified characteristic

Country	Participants
India	375 mums 375 dads 75 teachers
UK	225 mums 225 dads 75 teachers
China	225 mums 225 dads 75 teachers
Australia	225 mums 225 dads 75 teachers
South Africa	225 mums 225 dads 75 teachers
Indonesia	225 mums 225 dads 75 teachers
Saudi Arabia	225 mums 225 dads 75 teachers

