	48	SD	I have the materials in my home to disinfect surfaces in my home.	I have the materials at my school to disinfect surfaces in the classroom .
Social influences (Those interpersonal processes that can cause individuals to change their thoughts, feelings, or behaviours)	49	H	People around me (such as my partner, family and friends) remind children to wash their hands.	My colleagues remind pupils to wash their hands.
	50	H	Most people in my culture practice good handwashing habits.	Most people in my culture practice good handwashing habits.
	51	H	(RS) It doesn't matter how clean my children's hands are if other people's children are not.	(RS) It doesn't matter how clean my pupil's hands are if other children's are not.
	52	SD	People around me (such as my partner, family and friends) encourage me to disinfect my home.	My colleagues encourage me to disinfect the classroom .
	53	SD	(RS) Few people around me (such as my partner, family and friends) disinfect surfaces in their homes.	(RS) Few of my colleagues disinfect surfaces in the classroom .
Self Confidence Questions		Self confidence	When your [children/pupils] can see you watching them, what percentage of the time do they wash their hands with soap and water after going to the toilet and before eating? [response options 0 - 100%]	When your [children/pupils] can see you watching them, what percentage of the time do they wash their hands with soap and water after going to the toilet and before eating? [response options 0 - 100%]
		Self confidence	When your [children/pupils] cannot see you watching them, what percentage of the time do they wash their hands with soap and water after going to the toilet and before eating? [response options 0 - 100%]	When your [children/pupils] cannot see you watching them, what percentage of the time do they wash their hands with soap and water after going to the toilet and before eating? [response options 0 - 100%]
		Self-confidence	What percentage of the time do you wash your own hands with soap and water after going to the toilet and before eating? [response options 0-100%]	

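### The overall regression has no country terms, so its slopes mix within-country and between-country association without saying which is meant

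*Combined protocol and SAP*

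**What the plan says.** The second secondary hypothesis (Section 5b) is that the domains predict self-reported confidence "well as a whole and across each country/region". Section 12b tests it by regression: "Multiple regression analysis will be conducted, overall and for each country". The predictors are participants' "average responses to each behavioural determinate, and the outcome will be" the average of the confidence items. "An alpha value of 0.05 will be used to assess each" predictor. The documents mention no country indicator, random effect, centring on country means or clustered standard error.

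Country is nevertheless part of the design. The survey company will "recruit participants according to a stratified fashion across countries and demographic characteristics", and Table 2 in Section 11 sets 825 respondents for India and 525 for each of the other six countries.

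On exploratory work, Sections 1, 2 and 4 plan to compare responses across countries. Section 5c names countries for the surface items, but for hand hygiene it names only individual differences. The exploratory paragraph of Section 12b also names only individual differences and adds: "Their content is not further specified within this protocol".

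**The concern.** Suppose the average score on a domain and the average confidence both differ between countries. A pooled model without country terms then gives that domain a slope even if, inside every country, people who score higher are no more confident. That part of the slope rests on seven averages, weighted by quota rather than by any stated population, while the ordinary standard error treats it as resting on 3,975 independent people.

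Section 12b judges each predictor by significance at 0.05. With a sample this large, slopes too small to matter can pass. A domain could be reported as predicting confidence overall when the association lies only between country averages, and nothing in the plan would warn the reader.

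**Working it through.** **The plan's own figures.** Section 12a gives no power, effect size or between-country variance for the regression, so there is no calculation to reproduce. From Table 2:
- N = 825 + 6 × 525 = 3,975. India contributes 825/3,975 = 20.8% and each other country 525/3,975 = 13.2%.
- The overall model has 11 slopes and an intercept, so residual degrees of freedom are 3,975 − 12 = 3,963.
- Counting the residual variance, it has 13 parameters. The rule of 10 to 20 participants per parameter in Section 12a then asks for 130–260. With six indicators there are 19 parameters, needing 190–380. Both are far below 3,975.

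**Assumption.** Let ICC be the share of variance that lies between countries, taken equal for predictors and outcome, at 0.02, 0.05 and 0.10. These values are assumed.

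**Hand check, one predictor with a true within-country slope of zero.** If the seven country means of domain and outcome correlate r_b, then
- pooled r ≈ r_b × ICC, and z ≈ r × √N / √(1 − r²).
- Example: ICC 0.05 and r_b 0.5 give r = 0.025, z = 1.58 and a 35% chance of p<0.05.

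A correlation of that size arises easily by chance: seven independent pairs have a correlation with SD about 1/√6 = 0.41. Averaging over it, z has variance about 1 + N × ICC²/6:
- ICC 0.02: 1 + 0.265, SD 1.125; chance that |z| > 1.96 is about 8%.
- ICC 0.05: 1 + 1.656, SD 1.630; about 23%.
- ICC 0.10: 1 + 6.625, SD 2.761; about 48%.

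**Simulation of the planned model.** 11 predictors, within-country correlation 0.4 between them, all within-country slopes zero, ordinary least squares with and without six country indicators. Where repeated runs differed, the range is shown.

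| Country shifts | ICC 0.02 | ICC 0.05 | ICC 0.10 |
|---|---|---|---|
| One common shift on all domains | about 5% | about 5% | about 6% |
| Same shift shared by domains and outcome | 5–6% | 7% | 12% |
| Independent shift in each domain (extreme) | 8–9% | 21–24% | 40–42% |
| Six country indicators, any setting | about 5% | about 5% | about 5% |

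At ICC 0 the rate is about 5% with or without indicators. Across the settings without indicators, the median absolute standardised slope is 0.013–0.031, against 0.013 at ICC 0, and the median R² is 0.3–1.6%.

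**One concrete source.** Section 11 says "Some items will be reverse scored to mitigate acquiescence bias". In Appendix A, 17 of the 33 hand-hygiene items are reverse-scored: two of three in six domains and one of three in five. Agreement style therefore does not cancel within a domain. A shift of d points moves a domain average by d/3, up in five domains and down in six. With an assumed between-country SD of 0.3 points, the averages move by 0.10; at a domain SD of 0.6–1.0 this is a predictor ICC of about 0.01–0.03. The rejection rate is then about 7%, 9–11% and 12–18% at outcome ICCs of 0.02, 0.05 and 0.10. The confidence items ask "what percentage of the time do they wash their hands with soap and water" or a similar percentage question, so agreement style need not shift the outcome itself.

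**Power.** For a true within-country slope of 0.05, power is 71% without and 70% with indicators at ICC 0. At ICC 0.05 with independent shifts it is 63% and 72%.

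**The case against.** The strongest reply is that the hypothesis is about prediction in the whole sample. A total association answers that, and the seven country regressions already supply the within-country answer. Much of this stands. A total association is a legitimate target, and for that target the rates above are not error rates: they apply to the within-country reading. But the plan does not say that a total association is intended. Even if it is, the between-country part depends on quota weights and on seven averages. The ordinary standard error is too small for any claim that reaches beyond these seven countries.

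It is also fair that every ICC is assumed, that one common shift does almost no harm, and that 3,975 is the planned maximum, since Section 11 closes a country after 30 days even if its quota is unmet.

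A reader might infer three stronger things that do not hold:
- **A domain significant only without indicators is linked to confidence only between countries.** Loss of significance does not show that. In simulations with independent shifts, a true within-country slope of 0.03 was significant only in the unadjusted model in about 9–31% of runs, and a slope of 0.05 in about 5–15%.
- **A wrong list of predictive domains would steer the school intervention.** Section 2 ties the intervention to the most common reasons and to the survey results in general, not to this regression.
- **The exploratory sections contradict each other.** Section 5c leaves country out for hand hygiene, which is an omission in work that the plan openly leaves unspecified. It does not justify a formal programme of measurement-equivalence testing.

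**Conclusion.** The point holds for the overall regression only. As written, its slopes mix two kinds of association and its standard errors overstate what is known about one of them. Under assumed ICCs of 0.02–0.10, the chance that a domain with no within-country link reaches p<0.05 runs from about 5–6% (one common shift) to about 8–42% (independent shifts, the extreme case). Which end is nearer the truth cannot be told from the documents. The spurious slopes are small, the analysis is half of one secondary hypothesis, and neither the primary factor analysis nor the country regressions are touched. It is worth correcting because the correction is nearly free, not because the analysis fails without it.

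**What to change.** In Section 12b:
1. Add six country indicators to the overall regression and state that its coefficients are within-country associations.
2. If the total association is also of interest, report the model without indicators as a sensitivity analysis, labelled as mixing within- and between-country differences. State that a change in significance between the two models will not be read as evidence that a link is only between countries.
3. Show the seven country slopes beside each overall slope. A domain-by-country test (6 degrees of freedom) may accompany them as a descriptive aid. At a level of 0.05/11, a slope of 0.2 in three, two or one of the 525-person countries and zero elsewhere is detected with about 88%, 77% or 41% probability, so the test should not decide what is shown.

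Minor: align Sections 1, 2, 4, 5c and 12b on whether hand-hygiene responses are compared across countries. Any such comparison should carry a caveat that differences may reflect translation or response style.

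Cost: a few lines of text, a little analysis time and no new data, because country is a recruitment quota. Residual degrees of freedom fall from 3,963 to 3,957. The adjusted slopes no longer describe differences between countries, which is why the unadjusted model may be worth keeping as a labelled sensitivity analysis.

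### The confidence regressions put ordinary multiple regression on a bounded 0–100% average with no guard against non-constant variance, so the 0.05 tests may miss their level in a direction the documents do not settle

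*Combined protocol and SAP*

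**What the plan says.** Section 12b, under regression analyses, states: "Multiple regression analysis will be conducted, overall and for each country". With seven countries that is eight fits. The predictors are the respondent's domain averages, and "the outcome will be participants' average responses to the confidence items". The testing rule is: "An alpha value of 0.05 will be used to assess each predictors' contribution to the overall model".

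Section 11 (Survey Section 5) and Appendix A define three confidence items. The first concerns "confidence about how often their children clean their hands when they are present, 0% to 100% of the time". The second concerns "confidence about how often their children clean their hands when they are not present, 0% to 100% of the time". The third concerns the adult's own handwashing. Appendix A gives the scale as "response options 0 - 100" per cent, so the average cannot go below 0 or above 100. For the predictors, section 11 says: "we aim to assess each of 11 behavioral determinates using at least 3 items", on five-point scales.

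Section 12b mentions no residual check, robust or bootstrap standard error, transformation or bounded-outcome model for this analysis. No section gives a pilot mean, standard deviation or share at 100% for the confidence items, or a distribution for the domain scores.

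**The concern.** Default regression standard errors assume the same residual variance for every respondent. A percentage capped at 100 can break that assumption. Where the expected score is close to the cap there is little room to vary, and further away there is more. If the determinants really move the expected score, the variance changes with the determinants too. The reported standard errors then do not describe the true sampling variation of the coefficients, and more respondents do not repair this, because the reported and true errors shrink together.

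At stake is the second secondary hypothesis in section 5b: which determinants are declared predictors of confidence, overall and by country, and how wide their intervals are. Section 12a says the sample size was designed to support this regression as well as the factor analysis.

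**Working it through.** **Inputs from the documents.** 11 domain averages of at least three five-point items; an outcome that is the mean of three 0–100% items; alpha 0.05 per predictor (two-sided assumed, since the side is not stated). From Table 2, n = 225 + 225 + 75 = 525 in six countries and 375 + 375 + 75 = 825 in India, so the pooled N is 825 + 6 × 525 = 3,975. Ceiling, skew and effect size are assumptions, varied over a range.

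**Where the error comes from.** Let r_i be what is left of one predictor after regressing it on the other ten, and σ_i² respondent i's residual variance.

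- Reported variance of the slope: about σ̄² / Σr_i², where σ̄² is the average residual variance.
- True variance: Σ(r_i² σ_i²) / (Σr_i²)².
- True / reported: Σ(r_i² σ_i²) / (σ̄² Σr_i²).

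The ratio exceeds 1 only if unusual predictor values (large r_i²) go with large residual variance. With mostly high, left-skewed scores, the unusual respondents are the low scorers, who sit away from the cap and vary more, so the ratio is above 1. With right-skewed scores the unusual respondents sit near the cap, so it is below 1. With symmetric scores the two tails cancel. If no determinant matters, σ_i² does not depend on the predictors and the ratio is 1.

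**Reproducing the plan's figure.** With almost no ceiling, ordinary tests rejected true nulls 4.5–5.2% of the time, so the stated 0.05 is reproduced.

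**Simulation with a ceiling.** Three items clipped to 0–100 and averaged; 11 correlated predictors. Except in the first row, five determinants are active and rejection is counted on the null ones. There were 2,000–3,000 runs at n = 525 and 500 at N = 3,975; the Monte Carlo standard error is 0.1–0.2 and 0.3–0.4 percentage points respectively.

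| Scenario | Ordinary rejection of true nulls | Reported SE / true SE |
|---|---|---|
| No determinant matters; 10%, 31% or 62% of averages at 100 | 4.9–5.2% | about 1 |
| Symmetric scores; 13–60% at 100 | 4.7–5.1% | 1.00 |
| Mild left skew | 4.9–6.4% | 0.94 or higher |
| Moderate left skew | 5.4–9.8% | 0.84 or higher |
| Strong left skew | 5.6–12.7% | 0.77 or higher |
| Right skew; 13–60% at 100 | 2.4–3.8% | 1.07–1.15 |
| N = 3,975, symmetric | 4.2–5.2% | about 1 |
| N = 3,975, left skew | 6.7–9.1% | 0.87–0.93 |

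The left-skew rows at n = 525 include weak signals (R² about 0.05), which alone give 4.9–6.3%. The 12.7% needs strong skew, R² of 0.26 and 61% of averages at exactly 100.

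**Consistency check.** If reported SE / true SE = k, the test should reject about 2Φ(−1.96k). For k = 0.768, 2Φ(−1.505) = 13.2% (simulated 12.7%). For k = 1.149, 2Φ(−2.252) = 2.4% (simulated 2.4%).

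**Other assumed set-ups, n = 525, three active determinants.**

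- Unobserved-child item set lower, latent R² 0.1 or 0.25, and 13%, 20% or 43% of averages at 100: symmetric 4.7–5.2%, mild left skew 5.0–6.3%, moderate 5.7–7.3%, strong 5.7–9.0%.
- Unobserved-child item set 20 points lower, latent R² 0.25, and 4–19% of averages at 100: 4.5–5.6% from symmetric to left-skewed scores.

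A further run of the three-item average at n = 525 gave 4.4–5.3% with symmetric scores and 5.2–8.7% with left skew and real effects. True standard errors of the active domains were 1–31% above those reported.

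**With HC3 standard errors** (each σ_i² replaced by the respondent's own squared residual, scaled up for leverage): 4.5–5.2% at n = 525 and 4.3–5.4% at N = 3,975 in the main simulation, and 4.1–5.5% across the other runs in which it was applied.

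**The case against.** A reader might infer that confidence scores will pile up at 100%, and that the standard errors are therefore too small and the tests above 5%, overall and in every country. The documents do not support that. They give no share at 100%, and pile-up alone does not inflate the tests, as the first two rows of the table show. Averaging also thins the ceiling: with 59% of single answers at 100, only 31% of three-item averages were at 100. One item asks about children the adult cannot see, where lower answers are plausible. All of this stands.

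It is also fair that the analysis is secondary, that a test at 6% rather than 5% would seldom change which determinants are reported, and that naming multiple regression does not forbid residual checks or robust errors.

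Two things remain. First, the conditions for inflation are not far-fetched. Section 5b hypothesises that the determinants predict confidence well, so the case in which nothing matters is the one the plan expects not to see. Many Appendix A items, such as those on the parent's role, the ability to teach handwashing and running water at home, are ones most adults would plausibly endorse. That is inference from wording, not data, and some domains, such as Emotion, may be less skewed. Second, leaving the choice open means standard errors could be chosen after it is known which determinants are significant.

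**Conclusion.** The gap is real but minor. The plan fits ordinary regression to a bounded average and nothing in it protects the 0.05 tests against non-constant variance. Whether those tests are liberal, correct or conservative depends on distributions the documents do not give. Given a ceiling, mostly high domain scores and several determinants that truly matter, per-predictor tests run at roughly 5–9% in typical assumed scenarios and up to about 13% in the most extreme, with intervals too narrow to match. These figures rest on assumed ceilings, skew and effect sizes. The primary factor analysis is not affected. This is a cheap improvement to make before the data are seen, not a flaw that invalidates the regression.

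**What to change.** Add to section 12b that all tests and confidence intervals from the confidence regressions, overall and by country, use heteroscedasticity-robust (HC3) standard errors, or bootstrap standard errors where the model is fitted in AMOS. Add that the share of averages equal to 100% will be reported for each fit.

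The cost is one or two sentences and a software option. No item, sample size or coefficient estimate changes. Intervals become somewhat wider where the ordinary ones are too narrow. HC3 does not address a mean that bends as it approaches the bound; the reported share at 100% lets readers judge how much that could matter.
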